5.1 Study Calendar

Table 1: Study Schedule of Events (Healthy Volunteers)

Protocol Assessments	Visit 1 ¹	Visit 2 ¹	Safety Interview (Day 7)
	Screening (Day -28 to Day 0)	PET/CT scan (Day 0)	
Informed consent	X		
Medical History and Physical Examination ²	X		
Eligibility Assessment	X	X	
Urine Pregnancy Test ³	X	X	
Concomitant medications	X	X	
[¹⁸ F]F-AraG PET/CT imaging		X	
Adverse events collection ⁴		X	X ⁵

1. Visits 1 & 2 can be merged into a single visit done on the same day.
2. Includes vital signs, height, weight, BMI
3. In women of 18-60 years old unless documented hysterectomy or bilateral ovarian removal is available.
4. AE collection: Up to 2 hours of [¹⁸F]F-AraG infusion on Day 0; AEs that occur prior to this will be considered baseline.
5. The follow up safety interview can be performed telephonically and does not require a separate in-person visit.

Table 2: Study Schedule of Events (NSCLC subjects)

Protocol Assessments	Visit 1	Visit 2	Visit 3	Visit 4 ^Ψ	
	Screening (Day -28 to Day 0)	PET/CT scan (Day 0)	(Day 0-7)	PET/CT (7-14 Days after V3)	Safety Interview (7 days after last PET/CT scan)
Informed consent	X				
Medical history and Physical Examination ²	X				
Eligibility Assessment (including eligible lesions assessment)	X	X			
ECOG Performance Status Assessment	X				
SOC CT/MRI and/or FDG-PET/CT collection	X ¹				
Urine Pregnancy Test ³	X	X		X	
[¹⁸ F]F-AraG PET/CT imaging		X		X	
Administration of PD-1/PD-L1 Treatment			X		
Adverse events collection ⁴		X		X	X ⁵
Concomitant medications	X	X		X	

1. CT or MRI or FDG-PET/CT performed up to 45 days prior to Visit 2 is acceptable.

2. Includes vital signs, height, weight, BMI

3. In women 18-60 years old unless documented hysterectomy or bilateral ovarian removal is available

4. AE collection: Up to 2 hours of [¹⁸F]F-AraG infusion on Visits 2 and 4; AEs that occur prior to this will be considered baseline.

5. The follow up safety interview can be performed telephonically and does not require a separate in-person visit.

^Ψ Optional visit

5.2 Participant Duration

Healthy volunteer subjects will have up to 3 visits over a period of one to four weeks. NSCLC patients will have up to 4 visits over a period of one to four weeks, prior to and after cancer treatment.

We anticipate enrollment will be completed within 12 months after the start of enrollment and that the study will be completed in 2 years.

5.3 Participant Compensation

Participants will be compensated \$100 per PET/CT scan in the form of gift cards. The maximum total will be \$200 for NSCLC patients and \$100 for healthy volunteers.

6. MATERIALS AND METHODS

6.1 Study DRUG: [¹⁸F]F-AraG

6.1.1 Manufacture

[¹⁸F]fluoride (n.c.a.) in [¹⁸O]water is passed through a PS-HCO₃ cartridge, eluted with 1 mL of a phase transfer catalyst solution containing Kryptofix222 (15 mg) and K₂CO₃ 3.5 mg) in 10:1 acetonitrile/water. The K222/K[¹⁸F]F complex is heated and dried under Helium at 65 °C for 3 minutes, followed by heating at 95 °C for 1 minute. After cooling to ~50 °C, a solution containing [¹⁸F]F-AraG triflylate precursor (6 mg in 1 mL DMSO) is added to the reactor and the solution heated to 115 °C for 45 minutes. After cooling down to ~40 °C, to the reaction mixture was added sodium methoxide, and heated at 100 °C for 10 minutes. Reaction is cooled to 40 °C and after addition of 0.5 mL of 1 N HCl stirred at 95 °C for 10 minutes. The reaction mixture is then cooled to 30 °C and diluted with a solution of 0.5 mL of 1N NaHCO₃ in 9.5 mL of water (SV3). The solution in the reactor is transferred through 4 × C-18 cartridges via a V31 valve and collected in a waste container. The cartridges are backwashed to the reactor with 2 mL of methanol in the pre-HPLC tube. Methanol is removed under vacuum with the flow of helium at 90 °C for 13 minutes. After cooling the reactor to 30 °C water is added and the solution transferred through a 0.45 µm filter into a pre-HPLC container.

Crude [¹⁸F]F-AraG is injected on to a HPLC Luna C18 semi-preparative reversed-phase column (5 µm, 10 × 250 mm). The desired product fraction (R_t ~ 16 minutes) is collected into the round bottom flask pre-filled with 30 mL of water. The diluted fraction is passed through the C18 plus cartridges and rinsed with water (10 mL), then the trapped product is eluted by ethanol (1 mL) into a collection vial for subsequent dilution with saline (9 mL). [¹⁸F]F-AraG for Injection is prepared by then passing through a 0.22 µm Millex GV sterile filter to a pre-assembled septum-sealed sterile collection vial (30 mL) for filtration and sterilization. The final sterile empty vial, product needle, vent needle, 4 mm GV filter for vent and sterile GV filter (33 mm) are assembled in a sterile LFH (laminar flow hood). The final product is released compliant to release specifications as submitted to the FDA. No further testing is required at the research site prior to injection.

[¹⁸F]F-AraG will be supplied by Cellsight at no cost to study patients.

6.1.2 Availability

The [¹⁸F]F-AraG will be synthesized, on a per scan basis, under cGMP at one of CellSight's identified qualified production sites. All qualified production sites are FDA-approved clinical manufacturers of the tracer. Cellsight carries the IND. Cellsight submitted all the manufacturing CMCs to the FDA for all approved sites. As needed, the facility staff will be trained by Cellsight in synthesizing this radiopharmaceutical. Please refer to CellSight Pharmacy Manual.

6.1.3 Agent Ordering

The [¹⁸F]F-AraG will be individually requested per subject by Nuclear Medicine research coordinators or technologists, under the supervision of the Nuclear Medicine investigators, for synthesis under cGMP at the identified production site. Please refer to CellSight Pharmacy Manual.

6.1.4 Study Treatment Accountability

The Investigator or designee will verify the contents of each shipment against the shipping documents. A study treatment accountability log will be kept by the Investigator to maintain current and accurate inventory records (batch, expiry, and quantity) covering the receipt, dispensing and the destruction of all the study treatments.

At the conclusion of the study, or other situations as applicable (ex. site closure, IP expiry, etc.) the Investigator must agree to return or destroy all study materials as instructed by the Sponsor.

Please refer to CellSight Pharmacy Manual.

6.1.5 Dispensing [¹⁸F]F-AraG

The [¹⁸F]F-AraG will be ordered and synthesized under cGMP at qualified sites by radiochemistry staff in the Nuclear Medicine department.

Each dose will be manufactured on a per patient, per scan basis, according to the investigator physician's prescription order. Upon receipt, qualified personnel will ensure that the study drug is delivered in good condition, inventoried, stored properly, labeled and dispensed in compliance with the pharmacy manual, all regulatory agencies and per the investigator physician's prescription order.

The [¹⁸F]F-AraG dose will be measured by the qualified personnel in a dose calibrator prior to dispensing. Then the syringe will be placed in a shielded carrier for administration via venous infusion. After the dose administration, the qualified personnel will return the syringe for residual measurement by the nuclear medicine technologists at the site. Measured radioactivity values and times of measurement will be documented, as well as the total injected volume.

Regulatory agencies require accounting for the disposition of all investigational drugs received by each clinical site. Information on drug disposition required by law consists of the date received, date dispensed, quantity dispensed, and the patient identification number to whom the drug was dispensed. The Investigator is responsible for accounting for all unused study drug and destroying all used study drug containers in compliance with the pharmacy manual.

6.2 uEXPLORER PET/CT Scan

For the purpose of this study, [¹⁸F]F-ArA/G PET/CT scan images must only be acquired on the uEXPLORER scanner and that scanner must undergo regular Quality Control (QC) checks. Documentation of such QC activities must be available upon request or audit. Image acquisition will be obtained in list mode and the raw data saved to allow for virtual radioactive dose reconstruction at a later date.

7. RISKS TO SUBJECTS

7.1.1 Risks from [¹⁸F]F-ArA/G PET/CT scan

In this study, 2-4 healthy subjects and 2-4 NSCLC patients will undergo research PET/CT imaging with [¹⁸F]F-ArA/G as specified in the experimental imaging section. [¹⁸F]F-ArA/G PET imaging has been performed on 6 healthy volunteers in a separate study with no drug-related side effects. In addition, [¹⁸F]F-ArA/G has been administered to 13 cancer patients with 7 of those patients getting two doses for pre and post immunotherapy scans, also without any drug-related side effects.

Given the prior clinical safety experience thus far, we expect few, if any, adverse effects from [¹⁸F]F-ArA/G administration in this study. Presently there are no standard surrogate biomarkers or imaging modalities that can substitute for these procedures. The alternative will be for the patient to withdraw from the imaging study.

The safety monitoring practices employed by this protocol are adequate to protect the subjects' safety and should detect all Treatment Emergent Adverse Events (TEAEs). An indirect health benefit to the subjects enrolled in this trial is the free medical tests received at screening and during the study.

Due to the (up to) 90-minute long scan time through which the participants are expected to remain still, the patients may feel discomfort and/or fatigue from laying on the scanner table. In addition, they may experience claustrophobia from being inside the scanner bore, which is a partially enclosed space.

Another risk is possible bruising and/or infection at the IV site.

Reproductive Risks are associated with PET: (PET) radiotracers studies on the fetus (unborn child) have not been done. To avoid risk to the fetus, it is important that female participants not become pregnant while they are participating in this research study. Avoiding sexual activity is the only certain method to prevent pregnancy. However, if they choose to be sexually active, they should use an appropriate “double barrier” method of birth control (such as female use of a diaphragm, intrauterine device (IUD), or contraceptive sponge, in addition to male use of a condom) or the female should be using prescribed “birth control” pills, injections, or implants. Such birth control methods should be used for as specified by their doctor prior to beginning their participation in the research study and continues for as long as specified by their doctor after their final study visit. If they choose to be sexually active during this study, even with the use of these birth control measures pregnancy could still result. The risks of participation in the research PET studies while pregnant include potential loss of pregnancy or possible birth defects. If participant is a woman 18-60 years old, they will undergo a urine pregnancy test within 24 hours prior to each PET session unless documented hysterectomy or bilateral ovarian removal is available. If participant becomes aware that they are pregnant during the course of their participation in this study, they should contact immediately the study doctor.

It is possible that uEXPLORER PET/CT scans may detect false positive findings that may require further follow-up (clinical, imaging or surgical) with all the risks associated with these follow-up procedures. The PET/CT images created for this study are for research and are not meant to evaluate subject health, as they would be if they were part of a clinical (non-research) visit to the doctor or hospital. The images will not receive any routine clinical review by radiologists who interpret PET/CT scans. This means that some findings may be overlooked or misinterpreted. However, if the PET/CT technologists do notice findings that cause concern, they will notify the Study Radiologist. Additionally, if a member of the research team notices any findings that cause concern while conducting image review for study purposes, they will notify the Study Radiologist. The Study Radiologist will conduct a brief review of part of the study images for quality purposes. If the Study Radiologist thinks a clinical problem is present, one of the IRB-approved study physicians will discuss these possible problems with the subject within 8 weeks or immediately upon recognition of any critical finding that requires immediate and/or urgent intervention as described in the Department of Radiology Critical Findings policy (full dataset of images are sometimes not available for review in less than 3 days). Upon written request, we will provide the subject with a copy of a subset of their CT images to take to the physician of their choosing. A subset of PET images may also be shared with the subject unless the images from the study are clinically uninterpretable. In addition, the sponsor may restrict sharing of PET images due to the nature of the research protocol or to protect intellectual property (e.g. proprietary radiotracers). We will send a standard letter to the designated licensed medical provider identified by the subject, unless one of the study physicians is part of the subject’s care. The standard letter will state that (i) the subject’s images were acquired exclusively for a research study and incidental findings that may be related to a medical condition were observed by a UC Davis radiologist; (ii) the images did not receive any dedicated

routine clinical review and findings may have been overlooked or misinterpreted; (iii) the subject's physician can contact the study doctor at any time if there are any concerns regarding the study or the subject's findings.

7.1.2 Radiation Risk

Each patient will receive up to two 5 mCi +/-20% doses of [¹⁸F]F-AraG. Dosimetry assessment estimated an effective dose of 0.58 and 0.62 mSv/mCi for males and females, respectively. Risks from the PET/CT itself include additional radiation exposure from the CT attenuation correction scan (estimated to be 10 mSv for each low dose CT scan and 1 mSv for each ultra low dose CT scan). The table below shows the estimated effective radiation dose received by the subjects in this protocol:

	Healthy Subjects	NSCLC Patients	NSCLC Patients who cannot undergo 90 minutes continuous scanning
Low dose CT scan	10 mSv	10 mSv	10 mSv
Ultra low dose CT scan	N/A	N/A	1 mSv
[¹⁸F]-AraG PET scan	2.9 +/- 0.29 mSv(male) 3.1 +/- 0.31 mSv(female)	2.9 +/- 0.29 mSv(male) 3.1 +/- 0.31 mSv(female)	2.9 +/- 0.29 mSv(male) 3.1 +/- 0.31 mSv(female)
Total estimated dose	12.9 +/- 0.29 mSv(male) 13.1 +/- 0.31 mSv(female)	12.9 +/- 0.29 mSv(male) 13.1 +/- 0.31 mSv(female)	13.9 +/- 0.29 mSv(male) 14.1 +/- 0.31 mSv(female)
Number of scans	1	2	2
Maximum estimated dose	13.2 mSv (male) 13.4 mSv (female)	26.4 mSv (male) 26.8 mSv (female)	27.4 mSv (male) 27.8 mSv (female)

The total estimated dose from the combined PET/CT examination will be 13.4 mSv or less for normal subjects and 27.8 mSv or less for patients with NSCLC. The use of radiation involves minimal risk and is required to obtain the desired research information.

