5. STUDY DESIGN

Protocol CST-FARAG-203 is a pilot study using the uEXPLORER total-body PET/CT system to acquire dynamic [¹⁸F]F-AraG scan data in healthy individuals and patients with NSCLC.

Screening will consist of eligibility confirmation, the patient signing the consent form, and any assessments outlined in the study calendars below. This will also include a query about status and date of COVID-19 vaccination.

Eligible healthy subjects will undergo a single dynamic [¹⁸F]F-AraG PET/CT scan (of duration up to 90-minutes) on the uEXPLORER PET/CT scanner within 28 days of screening or on the day of screening if possible and convenient to the subject. There will be a follow-up visit or call 7 days after the scan to assess any AEs that could be attributed to either the scan or the administration of [¹⁸F]F-AraG.

Eligible subjects with NSCLC who are planned to receive PD-1/PD-L1 immunotherapy will undergo a pre-therapy dynamic [¹⁸F]F-AraG PET/CT scan, and an optional post-therapy (first dose only) dynamic [¹⁸F]F-AraG PET/CT scan on the uEXPLORER total-body scanner.

For each enrolled patient, [¹⁸F]F-AraG will be administered by a licensed Nuclear Medicine technologist under the supervision of a board-certified Nuclear Medicine physician (ABNM or ABR certified) on an outpatient basis. It will be administered as a single bolus injection of 5 mCi +/-20% IV into a vein. Vital signs will be assessed just prior to and after completion of dynamic [¹⁸F]F-AraG PET scan.

For each scan, the subject will be prepared according to the site's standard procedures and asked to void the bladder immediately prior to imaging. For the scan, an intravenous (IV) line will be placed in a vein and the subject will be positioned supine on the scanner table. The PET/CT imaging will begin with a low-dose CT scan on the uEXPLORER PET/CT scanner. This CT scan will provide information for anatomic localization and attenuation correction purposes.

[¹⁸F]F-AraG will then be infused as above and a 90-minute dynamic PET scan will be performed on the uEXPLORER. The IV line will be removed after dynamic acquisition. For subjects who may not be able to undergo a 90-minute dynamic scan, a 60-minute dynamic PET scan will be performed, followed by a 10-minute static scan starting at 80 minutes post [¹⁸F]F-AraG infusion. The separate static scan at 80 minutes will be obtained along with an ultra-low-dose CT which is needed for attenuation correction of this separate scan.

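### The radiation table allows only ±10% on the tracer dose where the protocol permits ±20%, and counts the fallback CT once for two scans, so its stated maximum doses are too low.

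*Combined protocol and SAP*

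**What the plan says.** Section 5 sets the injected activity: "It will be administered as a single bolus injection of 5 mCi +/-20% IV into a vein". Section 7.1.2 repeats the tolerance: "Each patient will receive up to two 5 mCi +/-20% doses of [¹⁸F]F-AraG". Section 7.1.2 also gives effective doses of 0.58 mSv/mCi for males and 0.62 mSv/mCi for females, and CT doses "estimated to be 10 mSv for each low dose CT scan and 1 mSv for each ultra low dose CT scan".

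Section 5 describes a fallback: "For subjects who may not be able to undergo a 90-minute dynamic scan, a 60-minute dynamic PET scan will be performed". A 10-minute static scan at 80 minutes follows, with its own ultra-low-dose CT.

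The table in Section 7.1.2 has three columns. Its entries (male/female) are:

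| Column | PET dose per scan, mSv | Total per scan, mSv | Scans | Stated maximum, mSv |
|---|---|---|---|---|
| Healthy subjects | 2.9 ± 0.29 / 3.1 ± 0.31 | 12.9 / 13.1 | 1 | 13.2 / 13.4 |
| NSCLC | 2.9 ± 0.29 / 3.1 ± 0.31 | 12.9 / 13.1 | 2 | 26.4 / 26.8 |
| NSCLC, unable to do 90 minutes | 2.9 ± 0.29 / 3.1 ± 0.31 | 13.9 / 14.1 | 2 | 27.4 / 27.8 |

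The totals carry the same ± terms as the PET doses. The closing sentence turns the female maxima into limits for each group: the dose "will be 13.4 mSv or less for normal subjects and 27.8 mSv or less for patients with NSCLC".

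**The concern.** Two features of the table conflict with the text around it.

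First, the ± terms on the PET dose are 10% of the nominal values, whereas the activity tolerance is 20%. Every maximum in the table inherits the narrower band.

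Second, the fallback column shows 13.9/14.1 mSv per scan and two scans, yet its maximum of 27.4/27.8 mSv is less than twice that nominal total, before any upward tolerance is added. The column therefore contradicts itself.

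The closing figures are worded as upper limits. Subjects handled exactly as the protocol allows could exceed them. Section 8 says subjects gain no direct benefit, and Section 15.4 requires that potential risks be explained to each subject, so a stated dose limit ought to be right.

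**Working it through.** **Inputs.** Activity 5 mCi ±20%, so at most 6 mCi (Sections 5 and 7.1.2). Effective dose 0.58 (M) and 0.62 (F) mSv/mCi, low-dose CT 10 mSv each, ultra-low-dose CT 1 mSv each (Section 7.1.2). One ultra-low-dose CT per fallback scan (Section 5). One scan for healthy subjects, up to two for NSCLC patients.

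**Formula.** Maximum = number of scans × [CT dose + 5 × mSv/mCi × (1 + tolerance)], with a CT dose of 10 mSv for a 90-minute scan and 11 mSv for a fallback scan. All results below are male/female, in mSv.

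**Reproducing the stated figures.** Nominal PET dose: 5 × 0.58 = 2.90 and 5 × 0.62 = 3.10. The table's bands are 0.29/2.9 = 10% and 0.31/3.1 = 10%. At +10% the PET dose is 3.19/3.41, which gives:

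- Healthy: 10 + 3.19 = 13.19; 10 + 3.41 = 13.41 (stated 13.2/13.4).
- NSCLC, two 90-minute scans: 2 × 13.19 = 26.38; 2 × 13.41 = 26.82 (stated 26.4/26.8).
- Fallback column: 26.38 + 1 = 27.38; 26.82 + 1 = 27.82 (stated 27.4/27.8).

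So the printed maxima come from a ±10% band and, in the last column, one ultra-low-dose CT across two scans.

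**Check within the fallback column.** Two scans at the nominal per-scan total: 2 × 13.9 = 27.8; 2 × 14.1 = 28.2. Both exceed the stated maxima of 27.4/27.8.

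**Maxima with the protocol's inputs.** At +20% the PET dose is 6 × 0.58 = 3.48 and 6 × 0.62 = 3.72.

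| Case | Calculation | Result (M/F) | Stated (M/F) | Shortfall (M/F) |
|---|---|---|---|---|
| Healthy, one 90-minute scan | 10 + PET | 13.48 / 13.72 | 13.2 / 13.4 | 0.28 / 0.32 |
| NSCLC, two 90-minute scans | 20 + 2 × PET | 26.96 / 27.44 | 26.4 / 26.8 | 0.56 / 0.64 |
| NSCLC, two fallback scans | 22 + 2 × PET | 28.96 / 29.44 | 27.4 / 27.8 | 1.56 / 1.64 |

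All six stated maxima are too low. In the last row, 1.00 mSv is the missing CT and 0.58/0.62 mSv is the tolerance (2 × 0.29 and 2 × 0.31); rounding in the printed figures accounts for the remaining ±0.02.

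**When the closing limits are passed.**

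- 13.4 mSv, one 90-minute scan: (13.4 − 10)/0.62 = 5.48 mCi for a woman and 3.4/0.58 = 5.86 mCi for a man. Both lie inside the permitted 6 mCi.
- 27.8 mSv, two 90-minute scans: not passed, since the largest value is 27.44.
- 27.8 mSv, two fallback scans: (27.8 − 22)/(2 × 0.62) = 4.68 mCi for a woman and 5.8/(2 × 0.58) = 5.00 mCi for a man. A woman exceeds it at the nominal activity; a man exceeds it at anything above nominal.

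**The case against.** Two readings could be offered in defence of the table. The ± terms may express some other uncertainty, such as dosimetry, because Section 7.1.2 never says what they are. And the last column may mean one fallback scan plus one 90-minute scan, since a patient may be unable to lie still at only one visit. A single extra CT would then be deliberate.

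Neither reading rescues the limits. If the band is dosimetric, the maxima leave out the activity tolerance altogether and still do not cover 6 mCi. The mixed-scan reading is not stated, does not fit a column that gives a fallback total per scan and two scans, and is not the maximum. Even so, at +20% it gives 21 + 2 × 3.48 = 27.96 and 21 + 2 × 3.72 = 28.44 mSv, above 27.8 for both sexes.

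What does stand is that the error is modest. The 1.64 mSv excess needs a woman who takes the optional second scan, uses the fallback both times and receives 6 mCi both times, in a group of 2 to 4 patients. The 10 mSv per CT that dominates the total is itself a round estimate. The documents set no dose limit that the corrected values would cross, and nothing in them shows that the minimal-risk statement would change.

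**Conclusion.** The concern holds. The table uses half the permitted activity tolerance and omits one of two ultra-low-dose CTs, and the closing limits are below doses that the protocol allows. The largest excess over those limits is 0.32 mSv for healthy subjects (13.72 against 13.4, 2.4%) and 1.64 mSv for NSCLC patients (29.44 against 27.8, 5.9%). The NSCLC limit is at risk only when the fallback is used.

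These results rest on the protocol's own dose coefficients and CT estimates, on 6 mCi as the permitted maximum per injection, and, for the 29.44 figure, on the fallback being used at both scans. No objective, endpoint or analysis depends on these numbers. The point is a wrong safety figure, and it should be corrected.

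A separate matter of clarity is not part of the arithmetic error. Section 5 offers the fallback to subjects in general, while the table marks the ultra-low-dose CT as not applicable to healthy subjects. That restriction may be intended, since Section 2 expects healthy volunteers to tolerate the long scan better. If the fallback is open to them, their maximum is 11 + 3.48 = 14.48 (M) or 11 + 3.72 = 14.72 (F) mSv.

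**What to change.** In the Section 7.1.2 table:

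- Give the PET dose as 2.9 ± 0.58 (M) and 3.1 ± 0.62 (F) mSv, and carry ±0.58/±0.62 into the totals per scan.
- Double the whole fallback dose per scan, including its ultra-low-dose CT.
- State the maxima (M/F) as 13.48/13.72 mSv for healthy subjects, 26.96/27.44 mSv for two 90-minute scans and 28.96/29.44 mSv for two fallback scans.

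Restate the closing limits as 13.72 mSv for healthy subjects and 29.44 mSv for NSCLC patients.

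The alternative is to tighten the activity tolerance to ±10% in Sections 5 and 7.1.2. The fallback CT must still be counted twice, and the limits become 10 + 3.41 = 13.41 and 2 × (11 + 3.41) = 28.82 mSv. This changes operations for doses made scan by scan at a production site, so correcting the table is the lighter choice.

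Separately, say in Section 5 that the fallback is for NSCLC patients only, or add the healthy-subject fallback maximum (14.48/14.72 mSv at ±20%) to the table.

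The text change is one table and one sentence, plus a few words in Section 5. The stated maxima rise by about 0.3 to 1.6 mSv. Under Section 13.3 the change needs sponsor concurrence and, unless one of the listed exceptions applies, IRB approval before it is implemented. The sponsor should check whether the same figures appear in the consent form, which was not available for this review.
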